4.2.4. Treatment Phase

Treatment will be continued until progression of disease according to IMWG criteria, until the subject goes into transplant, unacceptable toxicities occur in individual subjects, or consent is withdrawn.

4.2.5.End of Treatment Visit

Subjects that discontinue from treatment will undergo an end of treatment visit, regardless of the reason of discontinuation, 30 (+/-7) days after the last dose of study medication.

4.2.6.Long Term Follow Up

Subjects will be followed up every 3 months for progression and survival after the end of treatment. Subjects will be followed for survival for up to 6 years after enrollment or until death, whichever occurs first. The follow up will be done over the phone.

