6.2.3. End of Treatment Procedures and Long-Term Follow-Up

Subjects who discontinue therapy for any reason must have and end of treatment (EOT) visit completed 30 days (± 7 days) after the last application of study drug. Following the end of treatment, subjects will be followed for survival for 6 years total since enrollment.

At the EOT visit, the subjects will undergo the following assessments:

Physical examination and vital

signs

- Body weight
- **ECOG**
- Blood pressure, pulse, temperature, respiration
- Physical examination

Pulse oximetry to investigator discretion

Hematology Hemoglobin, WBC with complete differential, RBCs,

> platelet count, absolute neutrophil and lymphocyte counts. WBC differential may be automated or manual as per

institutional standards.

Clinical chemistry Sodium, potassium, chloride, creatinine, glucose, uric

acid, phosphorus, magnesium, LDH, total bilirubin, CRP

Pregnancy test (if applicable) testing required **FCBP** pregnancy at treatment

> discontinuation and at 28-days following treatment discontinuation. If menstrual cycles are irregular, 14-days additional testing following treatment

discontinuation is required

Myeloma Disease Assessment-

laboratory

M-protein determination:

Serum Protein Electrophoresis (SPEP) and

immunofixation

- Urine Protein Electrophoresis (UPEP) and immunofixation
- 24hr Urine
- Serum Free Light Chains
- Serum quantitative immunoglobulins (Igs)

Bone Marrow Aspirate/biopsy

All BM aspirates and biopsies are SOC, except the end of cycle 4 sample, which will only be SOC for subjects who proceed to transplant. Quantify percent myeloma cell involvement, and obtain bone marrow aspirate for MRD analysis by flow and NGS. This is required at EOT (C12, C18 or C24), 24 months after C1D1, and yearly after that (for up to 6 years after enrollment). Additionally, a BM aspirate and biopsy is required at any time nCR is suspected and MRD will be tested at this time. If nCR (If nCR determination is not possible, then VGPR will be used to trigger a bone marrow biopsy. A Bone Marrow Biopsy to confirm nCR or VGPR will not be required if the subject is within 2 months of a landmark Bone Marrow Biopsy timepoint) is suspected within 3 months of EOT, it is acceptable to wait for the EOT BM biopsy.

For subjects who sign consent for correlative samples, an additional aspirate sample should be collected at EOT

CT-PET

MRD-negative subjects will undergo a yearly PET until

progression.

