6.4.2. Carfilzomib Administration

Carfilzomib for Injection is supplied as a lyophilized parenteral product in single-use vials. The lyophilized product is reconstituted with Water for Injection to a final carfilzomib concentration of 2.0 mg/mL prior to administration. The dose will be calculated using the subject's actual BSA at baseline. Subjects with a BSA > 2.2 m² will receive a dose based upon a 2.2 m² BSA. Dose adjustments do not need to be made for weight gains/losses of \leq 10%. Subjects with a Body Surface Area (BSA) of greater than 2.2 m² will receive a capped dose of 44 mg of carfilzomib (at the 20mg/m^2 dose level), 123.2mg of carfilzomib (at the 56mg/m^2 dose level), or 154 (at the 70mg/m^2 dose level).

Carfilzomib will be given as an IV infusion over 30 minutes on Days 1, 8, and 15 of a 28-day cycle. If the subject has a dedicated line for carfilzomib administration, the line must be flushed with a minimum of 20 mL of normal saline prior to and after drug administration. The dose will be administered at a facility capable of managing hypersensitivity reactions. Subjects will be prehydrated with 250mL normal saline or other appropriate IV fluid formulation on cycle 1 Day 1. Other hydration procedures will be optional and per the discretion of the treating physician. Subjects will remain at the clinic under observation for at least 1 hour following each dose of carfilzomib in Cycle 1 and following the dose on Cycle 2 Day 1. Subjects should be monitored periodically during this period for evidence of fluid overload. Serum chemistry values, including creatinine, must be obtained and reviewed prior to each dose of carfilzomib during Cycles 1 and 2. Refer to Table 6-1 for guidance regarding dose reduction in subjects with compromised renal function.

Doses of carfilzomib may be rescheduled up to 2 days if the scheduled day falls upon a holiday or with approval from the Lead Principal Investigator. Missed doses will not be replaced during a cycle. Carfilzomib will be escalated from 20mg/m^2 (Cycle 1 Day 1) to 56mg/m^2 (Cycle 1 Day 8 and 15 see below) and then further escalated to 70mg/m^2 (Cycle 2 Day 1) as long as the subject does not present with cytokine release symptoms (fever, rash, dyspnea, etc) after Cycle 1 Day 2.

- Cycle 1: 20 mg/m² Day 1; 56 mg/m² Day 8; 56mg/m² Day 15.
- Cycles 2 8: 70mg/m^2 if tolerated Days 1, 8, and 15
- Cycles 9+ (for up to 24 cycles max): 70mg/m² if tolerated Days 1 and 15

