6.5. Instructions for Initiation of a New Cycle

A new course of treatment may begin on the scheduled Day 1 of a new cycle if all of the following are met:

- ANC $> 1.0 \times 10^9/L$
- Platelet count $\geq 30 \times 10^9/L$
- Any other study drug-related adverse event must have resolved to grade 1 or baseline (see Appendix 2)
- Serum uric acid and creatinine concentrations must return to baseline prior to carfilzomib doses during Cycles 1 and 2

If these conditions are not met on Day 1 of a new cycle, the subject will be evaluated weekly, and a new treatment cycle will not be initiated until the toxicity has resolved, as described above.

If elotuzumab, carfilzomib or lenalidomide are held for the remainder of the previous cycle or the new cycle is delayed due to residual toxicity on the planned Day 1 of the next cycle, then the new cycle will be started at 1 dose decrement.

If a delay of starting a new cycle is greater than 21 days, the subject should be discontinued from treatment, unless continuing treatment is mutually agreed upon by the site Lead Principal Investigator at the University of Chicago and the Co-Investigator at the treating institution.

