6.6. Dose-Modification Guidelines

The following sections and tables summarize dosing modifications of elotuzumab, carfilzomib, lenalidomide, and dexamethasone to manage possible toxicity. Dose modifications different from those stated in the protocol should be discussed with the Lead Principal Investigator. Administration of carfilzomib and lenalidomide will be discontinued in the event of any other toxicity that, in the opinion of the Lead, Secondary Site, or Treating Investigator, warrants discontinuation.

In addition to dose reductions, administration of elotuzumab, carfilzomib and lenalidomide will be held temporarily in the event of a treatment-related toxicity at the Treating Investigator's discretion. Study treatment may be reintroduced if resolution of the event to the baseline value or to \leq Grade 1 within 21 days; otherwise study drug will be permanently discontinued. Any deviations from this plan must be approved by the Lead Principal Investigator.

If a subject's elotuzumab administration is delayed on day 1 of a cycle, carfilzomib, lenalidomide, and dexamethasone will also be delayed until the elotuzumab is resumed, which would then become the new day 1 of that cycle.

If a subject's elotuzumab is held in the middle of a cycle, carfilzomib, dexamethasone, and lenalidomide dosing will continue as scheduled. If the subject's elotuzumab is delayed during the cycle and is resumed within the designated window, (+/-3 days Cycles 1 and 2; +/-7 days Cycles 3 and beyond) the subject may receive the scheduled dose. If the elotuzumab is not resumed within the given window (+/-3 days Cycles 1 and 2; +/-7 days Cycles 3 and beyond), the subject is to omit that dose, and resume dosing at the next dosing time point.

If a study drug (except dexamethasone) is discontinued, the subject may continue on trial. However, if the discontinuation happens prior to the end of cycle 8 (1^{ary} endpoint), the subjects will Page 45

continue to be treated and will only be included on the intent to treat analysis.

All clinically-significant non-hematologic toxicities must be resolved to Grade 1 or baseline.

Dose reduction levels of elotuzumab, carfilzomib, lenalidomide, and dexamethasone for toxicity management of individual subjects are provided below:

Table 6-1 Carfilzomib Dose Adjustments

Nominal carfilzomib dose	Dose -1	Dose -2	Dose -3	Dose -4
70 mg/m^2	56 mg/m^2	45 mg/m^2	36 mg/m^2	27 mg/m^2

Table 6-1 Lenalidomide Dose Adjustments

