CrCl< 30 mL/min	Reduce lenalidomide to 15 mg every 48 h	Hold carfilzomib until CrCl> 30 mL/min. If attributed to carfilzomib, restart at 1 dose decrement. If tolerated, the reduced dose may be escalated to the previous dose at the discretion of the physician. If not attributed to carfilzomib, restart at dose used prior to the event. Frequent monitoring of renal function should then be implemented	Full Dose
CrCl< 30 mL/min requiring dialysis	5 mg once daily. On dialysis days the dose should be administered following dialysis.	Hold until resolved to ≤ Grade 2. Then restart carfilzomib at 1 dose decrement	Full Dose

Table 6-6 Dose Modifications for Non-hematologic Toxicity

	Recomme	nded Action	
Non-heme toxicity	Lenalidomide	Carfilzomib	Elotuzumab
Venous thrombosis/embolism ≥ Grade 3	Hold lenalidomide dose and adjust anticoagulation regimen; re-start at Treating Investigator's discretion at full dose	No adjustment required	No adjustment required
Hyperthyroidism or hypothyroidism	Omit lenalidomide for remainder of cycle, evaluate, and initiate appropriate therapy. Restart lenalidomide next cycle at 1 dose decrement	No adjustment required	No adjustment required
Congestive heart failure (CHF)	Any subject with symptoms of CHF, whether or not lenalidomide related, must have the dose held until resolution or return to baseline. If CHF was felt to be lenalidomide related, reinstate by one dose decrement after return to baseline. If no resolution of CHF after 2 weeks, the subject will be withdrawn from the study.	Any subject with symptoms of CHF, whether or not carfilzomib related, must have the dose held until resolution or return to baseline. If CHF was felt to be carfilzomib related, reinstate by one dose decrement after return to baseline. If tolerated, the reduced dose may be escalated to the previous dose at the discretion of the physician. If no resolution of CHF after 2 weeks, the subject will be withdrawn from the study.	Hold Upon resolution elotuzumab can be restarted at the treating physician's discretion
Hypertension including Hypertensive Crises	NA	≥ Grade 3: Carfilzomib attribution, hold drug until resolved to ≤ Grade 2. Resume at one level dose reduction	NA

Table 6-6 Dose Modifications for Non-hematologic Toxicity

	Recomm	ended Action	
Non-heme toxicity	Lenalidomide	Carfilzomib	Elotuzumab

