6.9. Treatment Discontinuation

Subjects will be free to discontinue treatment or withdraw from the study at any time, for any reason, or they may be withdrawn/ removed if necessary in order to protect their health (see reasons for withdrawal below).

Subjects will be removed from further treatment for the following reasons:

- Disease Progression
- Non-compliance with study procedures
- Subject no longer consents to participate in the study
- Intercurrent illness that interferes with study assessments
- Treatment-related toxicity requiring treatment discontinuation
- Incidence or severity of AEs that indicates a potential health hazard to the subject
- For the fourth occurrence of the same Grade ≥ 3 non-hematological toxicity
- A delay in treatment > 21 days unless approved by the Lead Principal Investigator as well that due to Congestive Heart Failure unresolved for > 28 days the treatment shall be discontinued (see table 6-7)
- Treating Investigator discretion
- Requirement for alternative therapy
- Suspected or positive pregnancy

• Termination of the study by the sponsor

The Lead Principal Investigator should be contacted regarding any impending discontinuation of a study subject. If the reason for withdrawal is the occurrence of an AE, the subject will be followed until such events resolve, stabilize, and, according to the Treating Investigator's judgment, there is no need for further follow-up. The reason for withdrawal from study must be documented in the case report form.

In case of premature discontinuation of the study treatment, the investigations scheduled for the EOT should be performed, if possible. Should a subject decide to withdraw, every effort will be made to complete and report the observations as thoroughly as possible. The Treating Investigator should contact the subject to determine as completely as possible the reason for the withdrawal. A complete final evaluation at the time of the subject's withdrawal should be made, with an explanation of why the subject is withdrawing from the study.

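### Version 8 gives sites conflicting instructions on four safety rules: unresolved CHF, cycle-2 dexamethasone, pregnancy-test sensitivity and contraception after treatment

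*Combined protocol and SAP*

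**What the plan says.** **CHF.** Table 6-6 (section 6.6.1.2) carries the same sentence in its lenalidomide and carfilzomib columns: "If no resolution of CHF after 2 weeks, the subject will be withdrawn from the study". Section 6.9, listing reasons for stopping treatment, says that "due to Congestive Heart Failure unresolved for > 28 days the treatment shall be discontinued (see table 6-7". The general limit is 21 days. Section 6.6 allows reintroduction if the event resolves "within 21 days; otherwise study drug will be permanently discontinued", adding that "Any deviations from this plan must be approved by the Lead Principal Investigator". Section 6.5 says "If a delay of starting a new cycle is greater than 21 days, the subject should be discontinued from treatment", unless the Lead PI and the treating co-investigator agree otherwise.

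**Dexamethasone, cycle 2, days 1, 8 and 15.** Section 4.2 confines the split dose to cycle 1 and gives 40 mg by mouth or IV on each treatment day of cycles 2-4. The synopsis, section 6.1, section 6.4.4, section 6.6.2 and Appendix 6 footnote 23 all apply the split to cycles 1 and 2: 20 mg IV before elotuzumab, then 20 mg by mouth the following day. A later sentence in 6.4.4 requires Lead PI approval for split dosing in any cycle except the first.

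**Pregnancy test.** Inclusion criterion 9 in section 5.1 requires a sensitivity of 25 mIU/mL. The synopsis version of the same criterion, and the screening procedures in 6.2.1, say 50 mIU/mL.

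**Contraception.** The synopsis and section 5.1 (criteria 10 and 11) require at least 28 days after leaving the study, with a latex condom for men. Section 6.3.2.1 requires 3 months after the last dose, with two concurrent methods for men.

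**The concern.** Sites act directly on these instructions, and following one section can put a site in breach of another. A site reading 6.9 could restart a subject who recovers from CHF after day 14, although Table 6-6 has already withdrawn that subject. A site reading 4.2 could give no IV dexamethasone before elotuzumab on three days of cycle 2, although Table 6-3 protects a 20 mg IV dose before elotuzumab from reduction. A site screening from 6.2.1 could clear a woman for lenalidomide with a test that does not meet the eligibility criterion. Subjects could be told different contraception periods and methods depending on the page used.

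At stake are subject safety and avoidable protocol deviations, not the statistical conclusions.

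**Working it through.** No design calculation applies. The check sets the texts side by side.

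**1. CHF.** Assume that all limits are counted from the same start of hold.

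| Source | Limit | Consequence |
|---|---|---|
| Table 6-6 | 14 days | withdrawal from the study |
| 6.5, 6.6 | 21 days (general) | treatment stops unless the Lead PI agrees |
| 6.9 | more than 28 days | treatment stops |

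- Gap between the two CHF-specific limits: 28 - 14 = 14 days.
- Days 15-21: 21 - 14 = 7 days in which 6.9 and the general limit would permit restart after recovery, and Table 6-6 would not.
- Days 22-28: 28 - 21 = 7 days in which restart would also need Lead PI agreement.
- Under Table 6-6 the 28-day clause is never reached.
- The elotuzumab cell of the CHF row has no time limit, so it does not settle the matter.

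**2. Dexamethasone, cycle 2, days 1, 8 and 15.**

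| | Section 4.2 | Five other places |
|---|---|---|
| Before elotuzumab | 40 mg, oral or IV | 20 mg IV |
| Next day | none | 20 mg oral |
| Weekly total | 40 mg | 20 + 20 = 40 mg |

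The total is unchanged. The dose and route before elotuzumab, and the next-day dose, differ on 3 days. Both schedules cannot be followed. Section 4.2 stands alone against five places. The approval sentence in 6.4.4 also contradicts that section's own standard split for cycle 2.

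**3. Pregnancy test.** 50 / 25 = 2, so the detection threshold in the synopsis and 6.2.1 is twice that of criterion 9. Section 5.3.1 makes Section 5 the eligibility standard, so 25 mIU/mL governs. Footnote 10 of Appendix 6 gives no value.

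**4. Contraception, in days from the last dose** (30-day months assumed).

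- 6.3.2.1: 3 x 30 = 90 days.
- 5.1, if leaving the study means the last dose: 28 days.
- 5.1, if it means the end-of-treatment visit, at 30 +/- 7 days: from (30 - 7) + 28 = 51 to (30 + 7) + 28 = 65 days.
- Break-even: 90 - 28 = 62 days. If a subject leaves the study more than 62 days after the last dose, 5.1 becomes the longer rule.

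The documents do not define the start point in 5.1, so the direction of the difference is not fixed.

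**The case against.** The strongest reply is that these are mostly editorial mismatches that careful sites can reconcile. Applying the stricter value satisfies both CHF rules and both pregnancy-test texts, and the longer period with the fuller set of methods would cover contraception. The Lead PI approves deviations and is contacted before any discontinuation, eligibility is reviewed centrally, and the mandatory Revlimid REMS programme binds subjects and prescribers. These controls reduce the risk, but nothing in the protocol text says which value a site should use.

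Several narrower objections stand:

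- Table 6-6 holds the three drugs until CHF resolves, so no reading treats active heart failure. The dispute concerns only restart after recovery.
- The 21-day limit is a general rule that the Lead PI can waive, not a third CHF rule.
- Section 4.2 gives the larger pre-elotuzumab dose, and 40 mg by mouth is the protocol's own premedication in cycles 3-4. In the randomized trial described in 1.5.1.1, 70% (23/33) of subjects with infusion reactions had them at the first dose, where 4.2 also gives 20 mg IV. Harm from the 4.2 schedule is therefore not shown.
- The cycle-1 day-22 route varies (IV in 4.2; oral in 6.1, 6.4.4 and footnote 23; ambiguous in the synopsis), but section 9.4 allows either route, so this is minor.
- The table citations are numbering slips. Section 6.4.2 says "Refer to Table 6-1 for guidance regarding dose reduction in subjects with compromised renal function", section 6.10.4 cites Table 6-7 for the same guidance, and both the renal and CHF rows are in Table 6-6.
- Version 8 is dated 26 March 2020, and section 4.2.3 planned a start in Q4 2016 with 12-18 months of enrolment. If accrual ran to plan, screening and cycles 1-2 were already over. The documents do not give actual accrual.

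A reader might also infer that withdrawal under Table 6-6 ends follow-up and so biases PFS or OS. The documents do not support this. Section 4.2.6 states "Subjects will be followed up every 3 months for progression and survival after the end of treatment" and section 6.2.3 states "Following the end of treatment, subjects will be followed for survival for 6 years total since enrollment". The wording in Table 6-6 is loose, but it does not override those provisions.

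**Conclusion.** The four conflicts are in current operative text and should be aligned.

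- **CHF:** 14 days against more than 28, affecting restart after recovery on days 15-21 without Lead PI agreement and on days 22-28 only with it. It would be tempting to say that sites may freely restart up to day 28; the 21-day rule prevents that.
- **Dexamethasone:** the only pair with no common solution. It affects 3 days of cycle 2, at an unchanged 40 mg weekly total.
- **Pregnancy test:** a two-fold difference, already settled in principle by criterion 9.
- **Contraception:** the durations, start points and men's methods differ. That 6.3.2.1 is always the longer rule cannot be claimed, because the start point in 5.1 is undefined.

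No endpoint, sample size or hypothesis test changes. The dexamethasone and pregnancy-test items matter only for subjects still to be screened or in cycles 1-2. The CHF and contraception rules stay live through E-Rd maintenance, because lenalidomide continues until progression. The CHF windows assume a common start of hold, and the contraception figures assume 30-day months.

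**What to change.** - **CHF:** put one limit in Table 6-6 and section 6.9, by default 2 weeks unless the sponsor's clinicians justify longer. State that treatment stops while follow-up for progression and survival continues. Cite Table 6-6 in 6.9, and correct the renal citations in 6.4.2 and 6.10.4 at the same time.
- **Dexamethasone:** change 4.2 to the cycle 1-2 split (20 mg IV before elotuzumab on days 1, 8 and 15; 20 mg by mouth on days 2, 9 and 16). Make the approval sentence in 6.4.4 refer to cycles other than 1 and 2. One stated route for cycle-1 day 22 would be tidy.
- **Pregnancy test:** change 50 to 25 mIU/mL in the synopsis and 6.2.1.
- **Contraception:** state one period of at least 3 months after the last dose, with one defined start point and one set of methods, in the synopsis, 5.1 and 6.3.2.1. If 5.1 was meant to run through follow-up, keep the longer period.

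The cost is one amendment and a site memo, plus consent wording if it repeats the contraception rule. No extra subjects or procedures are needed. The one clinical price is that, under a 2-week CHF limit, subjects who recover on days 15-28 cannot restart.

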6.6.2. Guidelines for Elotuzumab Infusion and pre-medication in Subjects with Infusion Reactions

Required Treatments

Dexamethasone

On weeks without elotuzumab administer the weekly dose of 40 mg (Cycles 3-4) or 20mg (Cycles 5+) dexamethasone orally on Day 1, 8, 15, and 22 (-1 to +3 days). At the investigator's discretion, the oral dexamethasone may be given as a split dose over 2 consecutive days each week.

At the discretion of the investigator, the oral dexamethasone component may be given as a split dose 12-24 hours and 3 hours prior to elotuzumab.

Premedication Before Elotuzumab:

1. Dexamethasone 20 mg IV (C1 and 2), 40mg PO (C3-4), or 20mg (C5+) not longer than 3 hours prior to the start of elotuzumab infusion when they coincide, and 20mg PO the day after elotuzumab infusion (C1-2 only).

AND

- 2. H1 blocker: diphenhydramine (25 50 mg PO or IV) or equivalent (45-90 minutes prior to the start of infusion)
- 3. H2 blocker: ranitidine (50 mg IV) or equivalent (45-90 mins prior to the start of infusion)
- 4. Acetaminophen (650 1000 mg PO), (45-90 mins prior to the start of infusion

Premedication Regimen in Subjects With a Prior Infusion Reaction

Subjects with prior infusion reaction must receive H1, H2 blockers and acetaminophen at maximum doses specified above.

Table 6-9 Elotuzumab infusion in subjects with infusion reactions

Prior Infusion Reaction	Corticosteroid premedication prior to elotuzumab
None or Only Grade 1 infusion reaction	no change
Prior Grade 2 infusion reaction	Split dexamethasone dose on days of elotuzumab; e.g. for dose level 40 mg to 28 mg prior to carfilzomib and 12 mg prior to elotuzumab
Prior Grade 3 or recurrent Grade 2 infusion reaction	8 mg oral dexamethasone (12 - 24 hrs prior to elotuzumab) AND 8 mg oral dexamethasone (at least 3 hrs prior to elotuzumab) AND 24 mg IV dexamethasone at least 45-90 min prior to elotuzumab

At the discretion of the investigator, the 40 mg oral dexamethasone component may be given as a split dose: 20 mg PO (12–24 hours prior to elotuzumab) AND 20 mg PO (3 hours prior to elotuzumab).

If a subject with a prior Grade 2-3 infusion reaction also requires dose reduction of dexamethasone, the weekly dexamethasone on the days of elotuzumab infusion should be no lower than 8 mg IV (on the day of elotuzumab infusion at least 45 minutes prior to elotuzumab). Subjects with a Grade 4 elotuzumab infusion reaction must have elotuzumab permanently discontinued. Additionally, subjects who have a recurrence of \geq Grade 2 infusion reactions with subsequent doses and subjects who have a true hypersensitivity reaction at \geq Grade 2 should have elotuzumab permanently discontinued (but may continue on KRd).

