6.4.4. Dexamethasone Administration

Dexamethasone will be administered no longer than 3 hours preceding elotuzumab and between 30 min and 4 hours prior to carfilzomib (on days that they coincide). When dexamethasone, carfilzomib and elotuzumab coincide, dexamethasone will be given first, followed by carfilzomib and finally elotuzumab will be infused:

- Cycle 1-2: 20 mg IV not longer than 3 hours prior to elotuzumab infusion and between 30 min and 4 hours prior to carfilzomib on Days 1, 8, and 15. 20mg PO will be taken on Days 2, 9, and 16 and 40mg PO will be taken as a single dose on Day 22 not longer than 3 hours prior to elotuzumab infusion.
- Cycles 3-4: 40 mg PO Days 1, 8, 15, 22. On days when dexamethasone coincides with elotuzumab, dexamethasone will be taken no longer than 3 hours prior to elotuzumab infusion. On days when carfilzomib is given, dexamethasone will be dosed between 30 min and 4 hours prior to carfilzomib
- Cycles 5+: 20mg PO Days 1, 8, 15, 22. On days when dexamethasone coincides with elotuzumab, dexamethasone will be taken not longer than 3 hours prior to elotuzumab infusion. On days when carfilzomib is given, dexamethasone will be dosed between 30 min and 4 hours prior to carfilzomib

Split weekly dosing on cycles other than cycle 1 (e.g. 10mg on Day 1 and 10mg on Day 2, etc.) is permitted with approval from Lead Principal Investigator

Dexamethasone given on days without elotuzumab or carfilzomib (on cycles 3+ day 22) may be self-administered by the subject on an outsubject basis.

Missed doses of dexamethasone will not be made up.

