Nominal Lenalidomide Dose	Dose -1	Dose -2	Dose -3
25 mg Days 1-21	15 mg	10 mg	5 mg

Table 6-3 Dexamethasone Dose Adjustments

Nominal Dexamethasone Dose	Dose -1	Dose -2	Dose -3
40mg or 20 mg	Reduce dexamethasone by 50% from starting dose; however, the 20-mg IV dose of dexamethasone given before the infusion on the day of elotuzumab infusions must not be decreased.	dexamethasone on the day when elotuzumab is	Discontinue dexamethasone

^{*}Split dosing of dexamethasone on days 1,2, 8,9, 15,16, 22,23 may be implemented to control toxicities that do not require a dose reduction. Split dosing requires the approval of the Lead Principal Investigator

6-4 Elotuzumab Dose Adjustments

No dose reductions for elotuzumab are allowed. If Elotuzumab is held on Day 1 of a new cycle, treatment with carfilzomib/lenalidomide/dexamethasone will also be delayed. If elotuzumab is held during any cycle on days 8, 15, or 22, the treating investigator will decide if lenalidomide, carfilzominb, and/or dexamethasone will be held using recommended guidance for retreatment below. Treatment may be delayed for a maximum of 21 days (see section 6.5.2.1 for details).

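### The dexamethasone instructions conflict on day window versus pre-carfilzomib timing, on who approves splitting, and on the Cycle 1-2 schedule including Day 22

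*Combined protocol and SAP*

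**What the plan says.** **Timing.** In weeks without elotuzumab, for Cycles 3-4 and 5+, section 6.6.2 (under its Required Treatments block) gives the weekly "dexamethasone orally on Day 1, 8, 15, and 22 (-1 to +3 days". The Cycle 3-4 and Cycle 5+ bullets of section 6.4.4 say: "On days when carfilzomib is given, dexamethasone will be dosed between 30 min and 4 hours prior to carfilzomib". The opening sentence of 6.4.4 words the same interval differently: "between 30 min and 4 hours prior to carfilzomib (on days that they coincide". Appendix 6 footnote 24 likewise attaches the interval to days on which the two drugs coincide.

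**Splitting.** Section 6.6.2: "At the investigator's discretion, the oral dexamethasone may be given as a split dose over 2 consecutive days each week". It adds a second discretionary option, under which "the oral dexamethasone component may be given as a split dose 12-24 hours and 3 hours prior to elotuzumab". Section 6.4.4 permits split weekly dosing in cycles other than Cycle 1 with Lead PI approval. The note to Table 6-3, on splitting to control toxicities that need no dose reduction, ends: "Split dosing requires the approval of the Lead Principal Investigator".

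**Cycles 1-2.** The premedication list in 6.6.2 gives 20 mg IV before elotuzumab and 20 mg PO the day after, with no exception for Day 22. Section 6.4.4 says that "40mg PO will be taken as a single dose on Day 22 not longer than 3 hours prior to elotuzumab infusion", and the 6.1 table also has 40 mg oral on Day 22. For Day 22 of Cycle 1, section 4.2 says 40 mg IV, Appendix 6 footnote 23 says 40 mg PO, and the synopsis allows IV (Cycle 1 only) or PO. Section 4.2 also gives an unsplit 40 mg, PO or IV, on Days 1, 8, 15 and 22 of Cycle 2.

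**The concern.** These are operative dosing instructions, and a site can reach a different regimen depending on which section it opens. On a carfilzomib day in a week without elotuzumab, a site using the 6.6.2 window could give the weekly dexamethasone the day before carfilzomib or up to three days after it. A site using the 6.4.4 bullets would record that as a deviation. A split made on site judgement under 6.6.2 lacks the approval that 6.4.4 asks for. On Day 22 of Cycles 1-2, dose and route before elotuzumab depend on the section followed.

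Five centers are planned (4.2.2), and deviations must be documented, major ones within 7 days (13.6.2). At stake are uniform treatment delivery and a deviation log that means the same thing at every site.

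**Working it through.** No statistical figure in the plan depends on this. The check compares the sections and counts infusions from the planned schedule.

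**1. Where the day window meets the pre-carfilzomib rule**

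Inputs: elotuzumab days from 6.4.1 and Appendix 6 footnote 19; carfilzomib days from 6.4.2 and footnote 20. Carfilzomib days that are not elotuzumab days:

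| Cycles | Carfilzomib | Elotuzumab | Carfilzomib without elotuzumab |
|---|---|---|---|
| 1-2 | 1, 8, 15 | 1, 8, 15, 22 | none |
| 3-8 | 1, 8, 15 | 1, 15 | Day 8 |
| 9+ (E-KRd) | 1, 15 | 1, 15 | none |

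Affected infusions as planned: 6 cycles × 1 = 6.

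- Through Cycle 8: 6 / (8 × 3) = 6/24 = 25%.
- Through Cycle 12: 6 / (24 + 4 × 2) = 6/32 = 18.75%.
- Through Cycle 18: 6 / (24 + 10 × 2) = 6/44 = 13.6%.
- Through Cycle 24: 6 / (24 + 16 × 2) = 6/56 = 10.7%.
- Subjects leaving for transplant after Cycle 4 (15 planned, section 1.7): Day 8 of Cycles 3 and 4 only, so 2 / (4 × 3) = 2/12 = 16.7%.

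With carfilzomib on Day 8, the window covers Days 7 to 11. Day 7 falls outside the 30-minute to 4-hour interval, and Days 9 to 11 fall after the infusion. Only a dose on Day 8 itself can satisfy both rules.

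**2. When elotuzumab is held or stopped**

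Sections 6.6 and 6.6.2.1 let carfilzomib continue when elotuzumab is held mid-cycle, and 6.6.2 lets subjects who permanently stop elotuzumab continue on KRd. Those weeks also become weeks without elotuzumab. The limiting case is elotuzumab stopped before Cycle 3 with carfilzomib given as planned: 6 × 3 = 18 of the 24 infusions through Cycle 8, plus 2 per E-KRd cycle from Cycle 9. This is an upper bound, not an expected count.

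**3. Who approves a split**

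| Section | Scope | Authority |
|---|---|---|
| 6.6.2 | weekly oral dose, weeks without elotuzumab, Cycles 3+ | investigator |
| 6.6.2 | oral component before elotuzumab | investigator |
| 6.4.4 | split weekly dosing, cycles other than Cycle 1 | Lead PI |
| Table 6-3 note | splitting to control toxicity without dose reduction | Lead PI |

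The first and third rows cover the same act and name different authorities. The Table 6-3 note is narrower and only partly overlaps.

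**4. Cycles 1-2**

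| Section | Day 22, Cycle 1 | Day 22, Cycle 2 | Days 1, 8, 15, Cycle 2 |
|---|---|---|---|
| 6.6.2 | 20 mg IV + 20 mg PO next day | same | 20 mg IV + 20 mg PO next day |
| 6.1, 6.4.4 | 40 mg PO | 40 mg PO | 20 mg IV + 20 mg PO next day |
| 4.2 | 40 mg IV | 40 mg PO or IV | 40 mg PO or IV, unsplit |
| Synopsis | 40 mg IV or PO | 40 mg PO | 20 mg IV + 20 mg PO next day |
| Footnote 23 | 40 mg PO | not stated | 20 mg IV + 20 mg PO next day |

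Two of the eight elotuzumab infusions in Cycles 1-2 fall on Day 22. The dose before those infusions is 20 mg or 40 mg depending on the section, but the total is 40 mg either way (20 + 20 = 40). The difference is therefore in pre-infusion amount and route, not in weekly dose.

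**The case against.** **The window is narrower than it looks.** A reader might infer that weekly dexamethasone can float throughout, including before elotuzumab. The text does not say that: the window is confined to weeks without elotuzumab from Cycle 3. The planned overlap is Day 8 of Cycles 3-8, and from Cycle 9 there is none as planned. This stands and sets the size of the point.

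**The sections can be read together.** The opening of 6.4.4 and footnote 24 apply the interval only when the drugs coincide, so a shifted dose might fall outside the rule. Carfilzomib may itself be rescheduled by up to 2 days (6.4.2), so the window might let the two drugs move together. Both readings are possible, but neither is stated. The 6.4.4 cycle bullets attach to any day carfilzomib is given, and the 6.6.2 window is not tied to a carfilzomib move. Footnote 24 is thus a source of ambiguity, not a separate contradiction.

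**Section 6.6.2 is headed for subjects with infusion reactions.** Its first block nevertheless sets required treatment and premedication generally from Cycle 1; subjects with a prior reaction have a separate subheading.

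**IV and PO are both allowed.** Section 9.4 says dexamethasone may be given either way, and the synopsis covers both routes for Cycle 1 Day 22. That softens the route conflict in Cycle 1. It does not resolve 20 mg against 40 mg before the infusion, or split against unsplit dosing in Cycle 2.

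**Harm is not shown.** A reader might infer that an infusion-toxicity objective is compromised. The safety objective and endpoint (2.2, 3.2) are general, the carfilzomib first-dose effect is described for Cycles 1-2 (6.10.2), and the window starts in Cycle 3. The documents give no reaction risk linked to dexamethasone timing on Day 8 of later cycles. This objection stands.

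**Conclusion.** The inconsistency is real on three points: the 6.6.2 day window against the 6.4.4 pre-carfilzomib bullets, investigator discretion against Lead PI approval for splitting, and the Cycle 1-2 schedule including Day 22. As planned, the timing conflict reaches 6 of 24 carfilzomib infusions through Cycle 8 (2 of 12 for subjects leaving for transplant after Cycle 4), with more only if elotuzumab is held or stopped while carfilzomib continues. These counts assume the planned schedule without delays and are opportunities for divergence, not predicted occurrences.

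The consequence is that sites can give different regimens and classify identical conduct differently. The primary test, its power and its error rate are untouched. Nor do the documents establish that 6.4.4 prevails over 6.6.2, or the reverse; they show only that both are current text. The point is modest, but worth correcting because it governs what sites do.

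**What to change.** Reconcile the synopsis, sections 4.2, 6.1, 6.4.4 and 6.6.2, the Table 6-3 note, and Appendix 6 footnotes 23 and 24, so that each of these has one instruction wherever it appears:

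- how the weekly day window and the pre-carfilzomib interval relate on a carfilzomib day without elotuzumab, including when elotuzumab is held or stopped;
- who approves splitting the dose, and in which circumstances;
- the Cycle 1 and Cycle 2 schedule, including dose, route and splitting on Day 22.

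Which rule, dose and route apply is for the sponsor to decide. The change is wording only and can go in one amendment, with the IRB approval that section 13.4 requires. It adds no visits, tests or subjects.
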